Tissue samples from patients undergoing surgery will be collected as follows: For the study population, the PI will collect any fresh tissue (adipose tissue) directly from theatre before fixing as it is not needed for establishing diagnosis and the uterine cancer tissue and lymph node will be collected by the PI after histo-pathological examination from the histo-pathology department after the diagnosis is established. For the control population, if they are having uterine surgery, then the PI will collect some endometrial tissue after histo-pathological examination from the histo-pathology department after the diagnosis is established. All tissue processing will adhere to Human Tissue Authority (HTA) guidelines and will be performed at the Oncology laboratory at Leggett building at University of Surrey.

For study population only - the patients will have repeat blood tests (30mls of venous blood taken each time) on day 1 post-surgery and at their 3 or 6 months routine post-surgery follow up appointment. Control population will not have any repeat blood tests.

For the study population, women who are recommended chemotherapy, we will also ask consent to collect demographic data and baseline blood sample (30mls venous blood) at the time of consultation and after 3rd and 6th chemotherapy cycles to assess any changes in the markers that may correlate with progression or regression of disease.

We will also obtain archival serum samples and tissue blocks (of uterine cancer patients consented from a previous study for use during an appropriate ethics committee approved research) to help increase the number of recruitments for this study. Their demographic data with identification log will be made available to the PI only to assess for correlation between their data and the tissue diagnosis during analysis.

Timing of events including telephone contact events:

- 1. Send study Invitation Letter with Appointment Letter.
- 2. Clinic visit where patient is recruited/ phone call follow-up after clinic visit if the PI is not able to attend the clinic.
- 3. Enrolment of participant in study after consent.
- 4. Collection of blood and tissue sample as described above.

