### 5.5. Data analysis

Standard statistical analytical tools will be used to analyse the data. Relation between different variables will be sought with odds ratio, confidence interval and significance with P value (<0.05 significant). The Mann–Whitney U test will be used to assess differential expression of immune markers between tissue types –blood and tumour tissue. Correlation with clinical characteristics will be determined using univariate log-rank and multivariable Cox proportional hazards adjusting for age, stage, grade and histology. Results will be compared between the study and the control populations.

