### 7.1. Inclusion criteria

- 1. Study population- Women diagnosed with endometrial cancer
- 2. Control population Women being seen in clinic for benign conditions
- 3. Age 18 or above
- 4. Of sound mind so they can give informed consent
- 5. Historical tissue sample/ blocks from previous cases in the oncology department in the Leggett building also be used if appropriate consent is in place.

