# 7.3. Sample size

We will aim to recruit 30-60 patients with diagnosed endometrial cancer in the study. This sample size will also include archived tissue sample (formerly consented and stored in Leggett building for use in future ethical research). We will aim to recruit as many patients in the control population as in the study population, aiming for a total (study + control population) of 100-120 patients.

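### Archived specimens enter the cancer group only, and the cancer-control comparison does not separate them from prospectively collected samples

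*Combined protocol and SAP*

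**What the plan says.** Section 5.1 (Study design) brings in material from an earlier study: "We will also obtain archival serum samples and tissue blocks (of uterine cancer patients consented from a previous study". The stated purpose is "to help increase the number of recruitments for this study". Section 7.3 (Sample size) sets the size of the cancer group, "We will aim to recruit 30-60 patients with diagnosed endometrial cancer in the study", and continues: "This sample size will also include archived tissue sample". Section 7.1, item 5, sets one condition for this material: "Historical tissue sample/ blocks from previous cases in the oncology department in the Leggett building also be used if appropriate consent is in place". No number or share of archived specimens is given. Nor is there a limit on storage time, a handling requirement, or a rule on when archived serum was drawn relative to treatment.

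No archived control material is described. Sections 5.1 and 6 have control blood drawn at a clinic appointment, and control endometrium obtained only from women who have uterine surgery during the study. Section 7.3 plans equal groups: "We will aim to recruit as many patients in the control population as in the study population".

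The first primary outcome in section 4.2 compares marker levels between the two groups. Section 5.5 (Data analysis) says only: "Results will be compared between the study and the control populations". The covariates named in sections 1, 4.2 and 5.5 are demographic, clinical and tumour characteristics. Sample source, storage time and assay batch are not among them, and no analysis without the archived specimens is planned.

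**The concern.** Six circulating markers are to be compared between women with and without endometrial cancer, with a view to diagnostic or prognostic use. If long storage or different handling raises or lowers a measured level, the change occurs only among cases. The cancer-control difference then combines biology with specimen history, and the planned analysis has nothing that would show how much is due to each.

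Timing adds to this. The study itself draws case blood at surgery, on day 1, at 3 or 6 months, and around chemotherapy. Nothing requires an archived serum sample to correspond to the pre-treatment draw.

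**Working it through.** **Inputs from the protocol.** There are 30-60 cases including archived material, with equal controls and a total of 100-120 (7.3); significance is at P<0.05 (5.5). Equal groups with 30-60 cases give 60-120 in total, so a total of 100-120 with equal groups means 50-60 per group. I therefore used 30, 50 and 60 per group. The protocol gives no effect size, SD or power, so there is no sample-size figure to reproduce.

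**Assumptions.** The archived share *f* is 25-50% of cases and the storage shift *s* is 0.5-1.0 SD; the documents give neither. Levels are normal with SD 1 within each source, and tests are two-sided. Section 5.5 names the Mann-Whitney test for blood against tumour tissue and names no test for cases against controls. I used it here as the nearest planned method.

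**Step 1: spurious difference.** With no true effect, the expected cancer-control difference is *f* × *s*. The range runs from 0.25 × 0.5 = 0.125 SD to 0.50 × 1.0 = 0.50 SD.

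**Step 2: false-positive rate.** I simulated 40,000 studies per scenario with no true difference, shifting only the archived cases. Each cell gives the spurious difference and the proportion of studies with P<0.05.

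| Per group | Archived cases | Shift 0.5 SD | Shift 1.0 SD |
|---|---|---|---|
| 60 | 15 | 0.125 SD, 10% | 0.25 SD, 22% |
| 60 | 30 | 0.25 SD, 25% | 0.50 SD, 71% |
| 50 | 13 | 0.13 SD, 9% | 0.26 SD, 20% |
| 50 | 25 | 0.25 SD, 22% | 0.50 SD, 62% |
| 30 | 8 | 0.13 SD, 7% | 0.27 SD, 14% |
| 30 | 15 | 0.25 SD, 14% | 0.50 SD, 40% |

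With no archived cases the rate is about 5% at every size. These are rates for one marker.

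**Step 3: can adjustment repair it?** Write the mean level as *a* + *b*·(case) + *c*·(archived). Every archived specimen is a case, so *c* is estimated only from archived against new cases. It measures storage only if those two sets of patients are otherwise alike. With no other covariates, *b* is then exactly the contrast of new cases with controls, so the archived cases add almost nothing to it. The clinical covariates the protocol names do not address the shift.

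**Step 4: power cost of a prospective-only comparison.** For a true 0.5 SD difference and *m* cases against *n* controls, the noncentrality is 0.5/√(1/*m* + 1/*n*), evaluated with the noncentral *t*.

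| Cases vs controls | Noncentrality | Power |
|---|---|---|
| 60 vs 60 | 2.739 | 78% |
| 45 vs 60 | 2.535 | 71% |
| 30 vs 60 | 2.236 | 60% |
| 30 vs 30 | 1.936 | 48% |
| 15 vs 30 | 1.581 | 34% |

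**The case against.** The strongest reply is that the amount of archived serum may be small. Serum is named explicitly only in section 5.1, whereas sections 7.1 and 7.3 speak of archived tissue and blocks. That stands: the share is unknown, the confounding is partial, and the rates above are conditional on assumed values.

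A second reply is that the study describes itself as exploratory, so pooling with a source flag and a prospective-only sensitivity analysis would also be defensible. That is fair, but the protocol plans neither, and a flag works only within the limits shown in step 3.

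A third is that restricting to prospective samples does not equalise handling. Case blood is drawn in theatre on the day of surgery and control blood in clinic. The protocol history also shows that controls were added by amendment, so earlier cases may have been stored longer. Both points stand as limits on the remedy.

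Three stronger readings are tempting but not supported:

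- **Assay batch is confounded with case status.** No ELISA plate layout is given, so archived and new samples could share plates. Section 5.4 plans a tissue microarray that makes staining uniform. Batch is an open risk. The microarray does not address storage age or serum.
- **Archived cases may have a different disease.** Section 5.1 calls the archived patients uterine cancer patients, but uses the same term for prospective cases, and section 7.3 counts archived material under diagnosed endometrial cancer. The terms appear interchangeable, so disease mixing is not shown.
- **The false-positive rate reaches 78%.** A *t*-test formula with unit SD gives this for a 0.50 SD difference at 60 per group. It ignores the extra spread from mixing sources: at *f* = 0.5 and *s* = 1.0 the case variance is 1 + 0.5 × 0.5 × 1² = 1.25. Simulating the mixture gives 71% with Mann-Whitney.

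**Conclusion.** The concern holds. Archived material enters the cancer group only and counts in its size, controls are all prospective, and the comparison does not separate sample source. A storage or handling shift in the archived cases would therefore bias the first primary outcome, and the planned analysis could neither detect nor fully remove it.

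The size is unknown because the protocol states neither the archived share nor any shift. Under the assumed ranges the per-marker false-positive rate is about 10-71% at 60 per group, 9-62% at 50 and 7-40% at 30, against a nominal 5%. If the archived serum is few in number or storage has little effect, the bias is correspondingly small. It should be corrected, and the change is inexpensive.

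**What to change.** - In section 5.5, record an archived/prospective flag and the storage time for every specimen. Make the cancer-control blood comparison on prospectively collected baseline samples the main analysis, with the pooled result as a sensitivity analysis.
- Use archived specimens in the within-case analyses (BMI, grade, stage, histology) with the flag included. State the number of archived serum samples and of archived blocks separately.
- In section 5.4, interleave cases and controls, and archived and new samples, across ELISA plates and microarray blocks.
- As a wording clarification only, tie item 5 of section 7.1 to item 1, so that archived cases are explicitly endometrial cancer.
- Report the theatre-versus-clinic difference in blood collection as a limitation, since none of the above removes it.

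The cost is protocol wording, two recorded variables, some laboratory planning and fewer cases in the main blood comparison. The power loss in step 4 is 7 to 18 percentage points at 60 per group (78% to 71% or 60%), and 14 points at 30 per group with half the cases archived (48% to 34%).

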# 5.2. Study flow-chart for patients undergoing surgery

Procedures	Pre-study	Treatment period		iod
	Screening	Day of Sx	Day 1 Post Sx*	3/6 months post-Sx FU*
Visit Number	1	2	3	4
Written informed consent	Х			
Demographic data	Х			
Medical history	Х			
Assessment of inclusion/ exclusion	Х			
criteria				
Protocol restriction and continued	Х	Χ	Х	Х
eligibility check				
Concomitant medication	Х	X	X	X
Taking blood sample		Χ	X	Х
Procuring tissue sample		X		
Recording AEs			Continuous	

\*post surgery bloods relevant for study population only

# 5.3. Study flow-chart for patients undergoing chemotherapy (CT)

Procedures	Pre-study	Treatment period		iod
	Screening	Before	After 3rd	After 4th
		starting CT	CT cycle	CT cycle
Visit Number	1	2	3	4
Written informed consent	Х			
Demographic data	Х			
Medical history	Х			
Assessment of inclusion/ exclusion	Х			
criteria				
Protocol restriction and continued	Х	X	Х	Х
eligibility check				
Concomitant medication	Х	Х	Х	X
Taking blood sample		Х	Х	Х
Recording AEs			Continuous	

### 5.4. Sample analysis

ELISA will be used to assay bio-marker levels in blood samples.

For tissue analysis we will set up a tissue microarray (TMA). This will allow more uniform staining of the sample for immunohistochemistry with no inter-specimen variation of the staining method. Each case will be reviewed, and the area of interest (tumour) marked on the slide. Cores from the areas of interest will be used to create the microarray block. Sections can then be cut from the microarray block and slides prepared for immunestaining. The advantage of using this method is that the samples are subjected to the same conditions while being stained and the same part of a tumour can be reliably stained for several markers. Tissue sections from the TMA will be used for immune-staining and the expression of the markers of interest will be scored.

Some tests have become available at the University of Surrey laboratory that can be done from the samples that are already being collected to maximise our information on endometrial cancer from the samples already available. These tests will be carried out at the University of Surrey laboratory and will not involve any resource implication on Royal Surrey NHS Foundation Trust.

The additional tests may include - looking at the cancer tissue microenvironment for infiltrating inflammatory cells and / or their secretions or any other adipocytokines. We may also look at the tumour microbiome to look for any commensal bacteria or micro-organism that may have a role in cancer onset, progression and drug response by secretion of small molecules and metabolites. Clinical data which is available on the cases will then be correlated with the histological and immunohistochemical results and statistical analysis will be carried out.

### 5.5. Data analysis

Standard statistical analytical tools will be used to analyse the data. Relation between different variables will be sought with odds ratio, confidence interval and significance with P value (<0.05 significant). The Mann–Whitney U test will be used to assess differential expression of immune markers between tissue types –blood and tumour tissue. Correlation with clinical characteristics will be determined using univariate log-rank and multivariable Cox proportional hazards adjusting for age, stage, grade and histology. Results will be compared between the study and the control populations.

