Also, in an inflammatory environment, macrophages secrete potent proinflammatory cytokines such as TNF- $\alpha$  and IL-6, which are known to activate numerous transcription factors that regulate the expression of genes involved in immune responses, anti-apoptosis,

angiogenesis, and metastasis. The mechanisms of tumorigenesis are thought to be involved are free-radical production that cause DNA damage and impaired DNA repair.

Research have further suggested that systemic levels of insulin-like growth factor (IGF) is dysregulated in obesity either due to increased IGF production or by down-regulation of IGF binding protein (IGFBP) prodution. IGF 1 is a growth and proliferation promotor and has inhibitory effects on cell death and is a major contributor in many neoplastic transformation.

The above biomarkers are physiologically interrelated and are likely to reflect a more restricted number of underlying biological pathways. Possibly, they work in a synergistic capacity to modulate the risk of developing endometrial cancer. If specific patterns of cytokine expression were found to be predictive of adverse outcome, then the specific receptors may be targeted as a therapeutic option for endometrial cancer. No study so far has looked at all these markers together in the serum and tissue samples of the same endometrial cancer patients to give a more wholesome idea about their effect on tumour genesis, progression and outcome. Therefore, this study is designed to assess the prognostic significance of these six biomarkers in the blood and tissue of endometrial cancer patients and co-relating the levels with their BMI and tumour type, after adjusting for age, parity, smoking status, menopausal status, use of Hormone Replacement Therapy (HRT)/ hormonal contraception, and prevalence of diabetes and hypertension.

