### 5. STUDY DESIGN and METHODS of DATA COLLECTION AND DATA ANALYSIS

# 5.1. Study design

All patients being referred to the Royal Surrey NHS Foundation Trust with diagnosed uterine cancer will be given the research information leaflet and invited to participate as the study

population of the research. Female patients being referred to Royal Surrey NHS foundation Trust for benign conditions (specifically not endometrial cancer) will be invited to participate as the control population.

Initially, an invitation letter will be sent alongside the patients' clinic appointment letter to inform them of the study and give them time for preliminary consideration of the study. Patients will then be approached in the outpatients' clinics after the initial consultation by the clinician. Alternatively, patients may be approached over phone and information about the study given at that time. The call will be scheduled after the clinic appointment visit so that the patient will have received the Invitation Letter that is sent out with the initial Appointment Letter, allowing patients sufficient time to consider the study. Patients will be given a participant information leaflet detailing the study rationale, methodology and analysis in clinic or alternatively the leaflet will be sent by post/ email (in case of telephone consultations). Patients who agree to participate in the study will be asked to sign a consent form after explanation at a later appointment.

Demographic data will be collected at the same time to correlate various risk factors associated with the development of uterine cancer. The data collected will include age, parity, smoking status, menopausal status, medications used, use of Hormone Replacement Therapy (HRT)/ hormonal contraception, and prevalence of diabetes and hypertension. This data will be collected by:

- Taking a medical history from the patient in clinic
- Patients' medical notes

This data will be directly entered into an existing departmental database for Gynaecological oncology which is password protected and stored on NHS computers.

Study participants will then have 30mls (2 ½ tablespoons) of venous blood taken on the day of the surgery and control participants will also have 30mls of venous blood collection alongside their clinic appointment.

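### The Mann–Whitney test of blood against tumour compares an ELISA concentration with a staining score in the same women, so its p-value depends on the unit chosen for blood

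*Combined protocol and SAP*

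**What the plan says.** Section 5.5 names one two-sample test and gives its contrast: "The Mann–Whitney U test will be used to assess differential expression of immune markers between tissue types –blood and tumour tissue". Results are called significant at P below 0.05. The section ends by promising a comparison of cancer patients with controls, but names no test for it.

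Section 5.4 fixes the two measurement scales. For blood, "ELISA will be used to assay bio-marker levels in blood samples". For tissue, "Tissue sections from the TMA will be used for immune-staining and the expression of the markers of interest will be scored". It gives no concentration unit, no scoring range and no standardisation that would put the two on one scale.

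Blood and tumour come from the same surgical patients. Section 5.1 has 30 mL "of venous blood taken on the day of the surgery", and for the same operation "the uterine cancer tissue and lymph node will be collected by the PI after histo-pathological examination". Section 1 presents the novelty of the study as looking at all six markers "in the serum and tissue samples of the same endometrial cancer patients". The study summary gives the aim as the relationship between marker levels in blood and in tissue, with a view to finding peripheral biomarkers.

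**The concern.** Mann–Whitney pools all values from two groups, ranks them together, and asks whether a value from one group tends to exceed a value from the other. That requires values that can be ordered against each other, and groups that are independent. Neither condition is met.

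- **Scale.** A concentration cannot be larger or smaller than a staining score in any meaningful sense. The ordering comes from the unit in which the concentration is written.
- **Pairing.** Each woman with both samples appears in both groups, so the groups are correlated.
- **Question.** For a peripheral biomarker, what matters is whether a woman's blood level tracks the expression in her own tumour. A test that discards the pairing cannot show this, and Section 5.5 names no other method that could.

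The risk is that most or all markers are reported as differentially expressed between blood and tumour, with very small p-values and no biological content, while the useful blood–tissue question goes unanswered although the data are there.

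**Working it through.** The plan gives no effect size, SD or power for this test, so there is no figure of its own to reproduce. The check was by direct calculation and simulation.

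**Inputs from the protocol.** Test and contrast (5.5); alpha 0.05, taken as two-sided because sidedness is not stated (5.5); ELISA for blood and a score for tissue (5.4); 30–60 cancer patients (7.3).

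**Assumptions, not from the protocol.** Blood lognormal with median 5 and log-SD 0.6; integer score 0–12 centred at 5; latent within-woman correlation 0.5.

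**Step 1: change only the unit.** The same simulated blood values were multiplied by 0.001, 1 and 1000. U counts the blood–score comparisons in which blood is larger, out of n².

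| Women | Blood × | U | U/n² | Mann–Whitney p | Signed-rank p | Spearman (p) |
|---|---|---|---|---|---|---|
| 30 | 0.001 | 30 of 900 | 0.03 | 5.3×10⁻¹⁰ | 3.7×10⁻⁹ | 0.336 (0.069) |
| 30 | 1 | 508 of 900 | 0.56 | 0.395 | 0.262 | 0.336 (0.069) |
| 30 | 1000 | 900 of 900 | 1.00 | 2.8×10⁻¹¹ | 1.9×10⁻⁹ | 0.336 (0.069) |
| 60 | 0.001 | 120 of 3600 | 0.03 | 1.1×10⁻¹⁸ | 1.9×10⁻¹¹ | 0.473 (0.00013) |
| 60 | 1 | 2031 of 3600 | 0.56 | 0.226 | 0.031 | 0.473 (0.00013) |
| 60 | 1000 | 3600 of 3600 | 1.00 | 3.2×10⁻²¹ | 1.6×10⁻¹¹ | 0.473 (0.00013) |

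The p-value and the direction both change with the unit. The signed-rank test fails in the same way, so pairing alone is no cure. Spearman ranks each measure separately and does not move.

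**Step 2: scales that do not overlap.** Then U = n², and the result depends on n alone:

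z = (n² − n²/2) / √[n²(2n+1)/12]

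- n = 30: z = 450 / √4575 = 450 / 67.64 = 6.65, p = 2.9×10⁻¹¹
- n = 60: z = 1800 / √36300 = 1800 / 190.5 = 9.45, p = 3.5×10⁻²¹

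No simulated data enter this step.

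**Step 3: pairing, supposing a common scale existed.** The test takes the variance of the group difference as proportional to 2/n. With within-woman correlation ρ it is proportional to 2(1 − ρ)/n. On a normal approximation the true size is therefore about 2[1 − Φ(1.96/√(1 − ρ))]:

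- ρ = 0.5: 1.96/√0.5 = 2.77, size about 0.006
- ρ = −0.3: 1.96/√1.3 = 1.72, size about 0.086

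Simulation (10,000 replicates; 2,000 for signed-rank power) agrees:

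| Pairs | ρ | Mann–Whitney size | Mann–Whitney power, 0.4 SD | Signed-rank power, 0.4 SD |
|---|---|---|---|---|
| 30 | −0.3 | 0.078 | 0.33 | 0.24 |
| 30 | 0 | 0.043 | 0.31 | 0.31 |
| 30 | 0.5 | 0.008 | 0.25 | 0.56 |
| 60 | −0.3 | 0.085 | 0.56 | 0.47 |
| 60 | 0 | 0.048 | 0.56 | 0.57 |
| 60 | 0.5 | 0.006 | 0.58 | 0.85 |

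The test holds its level only when blood and tumour are uncorrelated. It is conservative for positive correlation and anti-conservative for negative correlation, where its apparent power advantage reflects the inflated size.

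**The case against.** The strongest case on the other side has four parts.

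1. **The contrast is not a listed outcome.** Sections 4.2 and 4.3 list cancer versus control, additional tissue tests, correlation with obesity, tumour characteristics and treatment effect. The study is labelled exploratory. This is true and limits the reach of the error. But the study summary makes the blood–tissue relationship the aim, and being exploratory does not make a unit-dependent p-value interpretable.
2. **The pairing is incomplete.** The chemotherapy schedule (5.3) lists blood only, and archived serum and tissue blocks count towards the total (7.3), so some women may lack one sample. The number of complete pairs may be below 30–60, and the power figures above are best cases. Partial pairing still gives neither independence nor a common scale.
3. **The wording is loose.** The phrase about immune markers might cover the additional tests in 5.4, whose assays are not specified, or the authors might have meant cancer versus control within a sample type. The sentence nevertheless names blood and tumour as the two sides, and 5.4 describes no assay that measures both on one scale. If cancer versus control was meant, the text still has to change.
4. **The p-values come from assumed distributions.** This is correct: two other simulated sets of 30 women gave 0.14 and 0.45 in the middle unit. The individual values carry no weight. The dependence on the unit follows from how the test ranks, and Step 2 needs no simulation.

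**Conclusion.** The concern holds, and the sentence must be corrected before analysis. As written, the blood-versus-tumour test has no interpretable result: with nothing changed but the unit, p at 30 women runs from 0.395 to below 10⁻⁹ in either direction. That span rests on assumed distributions; the unit dependence does not. The scale mismatch is the decisive fault, since a paired test would not remove it.

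The pairing fault is secondary. Its size (0.6–0.8% instead of 5%; power 25% versus 56% at 30 pairs and 58% versus 85% at 60) applies only if a common scale existed, the within-woman correlation were 0.5, the shift were 0.4 SD and all pairs were complete.

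**What to change.** Replace the Mann–Whitney sentence in Section 5.5 with three rules, one for each type of comparison:

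1. **Blood against tissue in the same woman** (tumour, and adipose tissue or lymph node where these are measured): Spearman correlation with 95% confidence interval for each marker, using the day-of-surgery blood sample and stating the number of complete pairs.
2. **Independent groups on the same assay** (cancer versus control serum; tumour versus control endometrium score): Mann–Whitney, or regression adjusted for the confounders already listed in Section 4.2. This also supplies the missing test for the cancer–control comparison.
3. **Same assay repeated in the same woman** (day of surgery, day 1, 3 or 6 months; chemotherapy time points): Wilcoxon signed-rank, or a mixed model on the log marker.

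Six markers against three tissues make 18 correlations, so these should be presented as estimates with intervals rather than as a count of p-values below 0.05. Precision will be modest: by Fisher's transformation, an observed correlation of 0.3 in 30 pairs has an interval of tanh(0.310 ± 1.96/√27), that is −0.07 to 0.60.

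The cost is wording only: same patients, samples and software. Because Section 5.5 is protocol text, the change goes through the amendment route in Section 8.3.

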#### 3. THEORITICAL FRAMEWORK

As the incidence of endometrial cancer continues to rise there is a health need for a better diagnostic and prognostic approach.

Studying the different biomarker levels in blood and cancer tissue will enable us to look for new targets that may be useful in the treatment and prognostication of this cancer.

Also, if the levels of these markers change significantly post-treatment, we can investigate if it will be possible to use these markers to assess response to treatment as follow-up for risk of recurrence forms an important part of the treatment protocol.

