# 4.3. Secondary Outcomes

- 1. To determine if the markers have any prognostic significance by the expression profile with tumour grade, stage and histology.
- 2. To determine if the markers could be used as tools to assess effects of treatment.

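### Section 5.5 assigns clinical characteristics to log-rank and Cox models with no event defined, and the Cox model would not show how markers vary with stage, grade or histology

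*Combined protocol and SAP*

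**What the plan says.** Section 5.5 (Data analysis) gives the method for this question in one sentence: "Correlation with clinical characteristics will be determined using univariate log-rank and multivariable Cox proportional hazards adjusting for age, stage, grade and histology". The same section offers odds ratios, confidence intervals and P values for relations between unnamed variables, and ties the Mann–Whitney test to blood versus tumour tissue.

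The question is secondary outcome 1 in Section 4.3: "To determine if the markers have any prognostic significance by the expression profile with tumour grade, stage and histology". Section 1 puts a related aim as "co-relating the levels with their BMI and tumour type, after adjusting for age, parity, smoking status, menopausal status", and its list of adjusters continues with hormone use, diabetes and hypertension. Section 5.4 says that on the tissue microarray "the expression of the markers of interest will be scored" and that clinical data will be correlated with the results, without naming a method. For archived cases, Section 5.1 gives the purpose as "to assess for correlation between their data and the tissue diagnosis during analysis".

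On follow-up, the study summary enters the duration as not applicable. The last scheduled contact for surgical patients is a blood test at 3 or 6 months (Sections 5.1 and 5.2). The data items listed in Section 5.1 are baseline risk factors and medications, with no date of recurrence, progression or death.

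**The concern.** Log-rank and Cox analyses need a dated event, a time origin and a censoring rule. The plan supplies none, so an analyst following Section 5.5 has nothing to put on the left-hand side of the model.

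There is a second difficulty, which an endpoint alone would not cure. Secondary outcome 1 relates marker expression to grade, stage and histology. In the Cox model of Section 5.5 those three features are adjustment covariates, so the model would answer a different question.

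Unless this is settled beforehand, the endpoint, or the switch to a cross-sectional method, will be chosen once the data are in hand. With six markers and several tissues, that leaves wide room for selective reporting.

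**Working it through.** The plan states no power, effect size or event count for this analysis, so there is no figure to reproduce. The check is mainly one of reasoning, with some arithmetic on scale.

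**1. Is there an event anywhere?**

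| Place | What it offers | Event, origin and censoring defined? |
|---|---|---|
| Study summary | Follow-up duration not applicable | No |
| Section 1 | Prognostic significance and adverse outcome, as motivation | No |
| Section 3 | "follow-up for risk of recurrence forms an important part of the treatment protocol" | No |
| Sections 4.2 and 4.3 | No survival, recurrence or progression outcome listed | No |
| Section 5.1, chemotherapy samples | "to assess any changes in the markers that may correlate with progression or regression of disease" | No |
| Sections 8 and 8.7 | Prognostic outcomes to be inferred from generic data | No |

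**2. What would the Cox model estimate?** With marker m, the hazard is

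h(t) = h0(t) × exp(b1·m + b2·age + b3·stage + b4·grade + b5·histology).

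Here b1 is the marker's log hazard ratio with the other terms held fixed, and b3 is the log hazard ratio for stage with the marker held fixed. The quantity in secondary outcome 1 is the difference in mean m between stages (and likewise for grade and histology). The Cox likelihood takes all covariates as given, so that difference is not a parameter of the model. A marker could differ strongly by stage and still have b1 = 0.

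**3. Precision of a direct comparison.** Inputs: 30–60 cases (Section 7.3); significance at 0.05 (Section 5.5), taken as two-sided. Assumed: 80% power, no covariate adjustment, and a split between two groups from 50:50 to 20:80. Section 7.3 also aims for equal groups and 100–120 in total, which implies 50–60 cases.

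Detectable difference in SD = 2.802 / √(N·p·(1−p)), where 2.802 = 1.960 + 0.842.

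| Cases N | p = 0.5 | p = 0.2 | Range from exact t calculation |
|---|---|---|---|
| 60 | 2.802/√15 = 0.72 | 2.802/√9.6 = 0.90 | 0.74–0.92 |
| 50 | 2.802/√12.5 = 0.79 | 2.802/√8 = 0.99 | 0.81–1.01 |
| 30 | 2.802/√7.5 = 1.02 | 2.802/√4.8 = 1.28 | 1.06–1.33 |

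**4. Number of tests.** Six markers × three features × two compartments (blood, tumour) = 36 tests. If no marker were related to any feature, 36 × 0.05 = 1.8 would be expected below 0.05. Adding the adipose tissue and lymph node of Section 4.2 gives 6 × 3 × 4 = 72 tests and 3.6 expected.

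**5. How many covariates?** Age, BMI and a one-parameter feature make 3 terms, or 30/3 = 10 to 60/3 = 20 cases per term. All seven adjusters of Section 1 plus BMI and the feature make 9 terms, or 30/9 = 3.3 to 60/9 = 6.7. A feature with more than two categories lowers these figures.

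**6. Scale of a survival analysis.** Assumed: two equal marker groups and 80% power. The Schoenfeld formula, 4 × 2.802² / (ln HR)², gives 66 events for HR 2 and 27 for HR 3. The Freedman formula, 2.802² × ((HR+1)/(HR−1))², gives 71 and 32. At an assumed event fraction of 10–30%, 30–60 cases yield 30 × 0.10 = 3 to 60 × 0.30 = 18 events, or 0.6 to 3.6 events per term for five terms. Power for HR 2 is then 9% to 31%.

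**The case against.** A reader might infer that the plan has no means at all of answering secondary outcome 1. The documents do not support that. Section 5.5 also allows standard tools and odds ratios, and Section 5.4 promises correlation of clinical data with the immunohistochemistry. An odds ratio for high versus low marker by grade would be a legitimate cross-sectional analysis. What stands is narrower: neither sentence names variables, cut-points or a model, and the only sentence that assigns a method to clinical characteristics assigns log-rank and Cox.

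A reader might also extend the adjuster argument to both named methods. It applies to Cox only, because the log-rank test is described as univariate. That test still compares event times rather than marker levels, and it lacks an event in the same way.

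Thirdly, one might conclude that survival was never intended. That goes too far. The main clause of secondary outcome 1 speaks of prognostic significance, and Sections 1, 8 and 8.7 use outcome wording. If survival is meant, adjusting for age, stage, grade and histology is conventional. The defect under that reading is the missing endpoint.

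Finally, the study is labelled exploratory and this is a secondary outcome. That limits the weight of the point, but it does not make the named models runnable.

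**Conclusion.** The point holds and should be fixed before analysis. The log-rank and Cox analyses cannot be run as written, because no event, time origin, censoring rule or ascertainment is defined and follow-up is entered as not applicable. Were an endpoint added, the Cox model would still not estimate the relation of marker expression to stage, grade and histology. Both conclusions follow from the text and the form of the model, and need no assumed event rate.

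The precision figures do rest on assumptions about split, power and two-sided testing. They indicate that a direct comparison in 30–60 cases can detect only moderate-to-large differences, so results should be read as exploratory. The comparisons with controls and with BMI in Section 4.2 are unaffected.

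**What to change.** Replace the log-rank and Cox sentence in Section 5.5 with text such as:

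> In cases, marker level in blood taken before any treatment (log scale), or tumour tissue score, will be the outcome. Stage, grade and histology will each be the variable of interest, examined by a Kruskal–Wallis or trend test and then by linear or ordinal regression adjusted for age and BMI. Any further covariates from the Section 1 list will be few and named before analysis. Estimates with 95% confidence intervals and the number of tests will be reported as exploratory associations with established prognostic features.

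For surgical patients the relevant sample is the one described as "of venous blood taken on the day of the surgery"; the plan should state that it is drawn before the operation begins. Align the prognostic wording of Section 4.3 and the adjuster list of Section 1, which does not include BMI.

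If survival or recurrence is intended instead, define the event, time origin, censoring rule and data source (including archived cases) by amendment before analysis. Reconcile this with the follow-up entry in the study summary, and label the analysis exploratory, since at most 60 cases are likely to give few events.

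**Cost.** The cross-sectional option is a rewording through the amendment route in Section 8.3, with no new patients, samples or visits. Stage, grade and histology are already needed by the current model, but they should be added to the data items in Section 5.1. The price is that no survival-based prognostic claim can be made. Archived cases would contribute only where the three features are recorded and, for serum, where sampling before treatment can be shown, so the analysed number may fall below the planned 30–60. Tissue numbers may be lower still, because the chemotherapy schedule in Section 5.3 has no tissue collection. The survival option would also need status and dates for every case, and a check that consent and ethics approval cover their collection.
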